10. Subject has a history within the past 2 years or current diagnosis of significant psychiatric illness, per the most current version of the Diagnostic and Statistical Manual of Mental Disorders (DSM) (including but not limited to major depressive disorders and anxiety disorders) (subjects who are symptom free or with minimal limited symptoms may be included); or the subject has a current diagnosis or history of schizophrenia or bipolar disorder.
11. Subject has a relevant history of or current neurological disease other than preclinical AD, which may make interpretation of possible new neurological signs or symptoms difficult.
12. Subject has had a history within the last 5 years of a serious infectious disease affecting the brain (including neurosyphilis, meningitis, or encephalitis) or head trauma resulting in protracted loss of consciousness.
13. Subject has a history of epilepsy. Subject has a history of fits or unexplained black-outs other than vasovagal syncope within 10 years before screening.

14. Criterion modified per Amendment 5
  - 14.1 Subject has a hypopigmentation abnormality of the skin such as vitiligo at screening dermatological exam. Small localized lesions other than vitiligo are allowed.
15. Subject has any amyloid-related imaging abnormalities – edema or effusion (ARIA-E) at screening.
16. Subject has a clinically significant abnormal physical or neurological examination or vital signs at screening or baseline (Day 1 predose), which in the opinion of the investigator is not appropriate and reasonable for the population under study.
17. Criterion modified per Amendment 5
  - 17.1 Subject has, in the opinion of the investigator, a clinically significant 12-lead ECG abnormality (including left bundle branch block, atrioventricular [AV] block of second degree or higher, permanent pacemaker or implantable cardioverter defibrillator) at screening or baseline (Day 1 predose). The screening QTcF must be evaluated and must not exceed 450 msec in males or 470 msec in females. For triplicate ECGs, 2 of the 3 tracings must be below 450 msec in males or 470 msec in females. ECG recordings may be repeated once, and in the case of a question, a cardiologist and sponsor medical monitor should be consulted.

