Subjects approved for rescreening must sign a new ICF, and undergo appropriate screening evaluation according to the Time and Events Schedule, confirmed by the sponsor's medical monitor. This will include interim medical history, safety assessments, clinical laboratory assessments, and ECG. If MRI was completed within 6 months of randomization, it would not need to be repeated in most cases. If tests for amyloid accumulation (CSF, amyloid-PET or both), genomics and fluid biomarkers were completed and valid, they would not need to be repeated. Screening cognitive and other endpoint evaluations should follow the Time and Events Schedule; if screening cognitive evaluations were completed previously then testing in rescreening should be conducted 3 months or more after the prior testing.

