2.3. Reference Start Date and Analysis Phases

The analysis reference start date (Study Day 1) is defined as the date of the first dose of study medication. The Study Day of an event start or stop date is defined relative to the analysis reference start date as:

- Event date – analysis reference start date + 1, if the visit/event date is on or after the analysis reference start date, or

- Event date – analysis reference start date -1, if the visit/event date is before the analysis reference start date

Study Days <1 will be considered in the Screening analysis phase; Study Days \geq 1 (there is no Study Day 0) will be considered in the Double-blind analysis phase.

For visit dates prior to, or on, the date of the last dose of study medication, an Analysis Day will be defined as above relative to the analysis reference start date. For visit dates after the treatment end date, an Analysis Day is defined relative to the treatment end date as: Visit date – treatment end date + 1.

- Analysis reference start date (date of first dose as above) for all timepoints after first dose (whether before or after last dose)
- For assessments after last dose, use last observation before last dose as the reference time point.

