2.4. Visit Windows

As subjects do not always adhere to the protocol visit schedule, the following rules are applied to assign actual visits to analysis visits. Listed below are the visit windows and the target days for each visit. The same definitions will apply to visits before or after the treatment end date using the Analysis Day as defined in Section 2.3 above. The time period description will be appended with '(On-Trt)' for post-baseline visits on or prior to the treatment end date. The time period description will be appended with '(Off-Trt)' for post-baseline visits after the treatment end date. If a subject has 2 or more actual visits in one visit window, the visit closest to the target day will be used as the protocol visit for that visit window. The other additional visit(s) will not be used in the summaries or analyses but they can be used for determination of clinically important endpoints. If 2 actual visits are equidistant from the target day within a visit window, the later visit will be used.

All assignments will be made in chronological order. Once a visit date is assigned to a visit window, it will no longer be used for a later time point except for the endpoint. Listed below (Table 1) are the visit windows and the target days for each visit defined in the protocol.

Table 1: Visit Windows for on and off-treatment Analysis

Scheduled Visit Number	Time period (label on output)	Time Interval (Day*)	Target Time Point (Day)
7	Baseline	-120 to 1	1
8	Week 2	2 to 22	15
9	Week 4	23 to 36	29
10	Week 6	37 to 50	43
11	Week 8	51 to 64	57
12	Week 10	65 to 81	71
13	Month 3	82 to 106	92
14	Month 4	107 to 134	120
15	Month 5	135 to 165	148
16	Month 6	166 to 211	183
17	Month 8	212 to 256	239
18	Month 9	257 to 288	274
19	Month 10	289 to 333	302
20	Month 12	334 to 410	365
21	Month 15	411 to 501	456
22	Month 18	502 to 592	547
23	Month 21	593 to 683	638
24	Month 24	684 to 774	729
25	Month 27	775 to 865	820
26	Month 30	866 to 956	911
27	Month 33	957 to 1047	1002
28	Month 36	1048 to 1138	1093
29	Month 39	1139 to 1229	1184
30	Month 42	1230 to 1320	1275
31	Month 45	1321 to 1411	1366
32	Month 48	1412 to 1502	1457
33	Month 51	1503 to 1593	1548
34	Month 54	1594 to 1684	1639
	Month >54	1685 to ∞	1685

* Relative to analysis reference start date if visit date is prior to or on the treatment end date. Relative to treatment end date if visit date is after treatment end date.

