‘End point (On-Trt)’ is defined as the last available post-baseline result among the on-treatment visits. Unscheduled visit results are included in this definition and will be considered as the endpoint value if the unscheduled visit result is the last post-baseline result available among all on-treatment visits. ‘Baseline (Off-Trt)’ will be defined as the same as ‘End point (On-Trt)’. ‘End point (Off-Trt)’ is defined similarly to ‘End point (On-Trt)’ but based on off-treatment visits.

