6.4.3. MRI (Magnetic Resonance Imaging)

All subjects will have an MRI during screening and after randomization at Months 6, 12, 24, 36 and 54 (or at early termination, if not performed at the previous visit). MRI image evaluation will be performed by a core imaging laboratory.

The number and percentage of subjects with evidence of a finding at any time during the double-blind period and at each time point will be summarized by treatment group for each of the following:

- ARIA-E (Amyloid-related imaging abnormalities which represent vasogenic edema and related extravasated fluid phenomena), including parenchymal hyperintensity, sulcal hyperintensity, and gyral swelling.
- ARIA-H (Amyloid-related imaging abnormalities which represent microhemorrhages and hemosiderin deposits), including microhemorrhages (mH), macrohemorrhages, and superficial siderosis.
- Lacunar infarct
- Territorial infarct outside of the cerebellum
- Full territory cerebellar infarct

Similar summaries for ARIA-E and ARIA-H finding will be provided. A listing of the subjects with any of the findings listed above will be provided.

Similar analyses will be performed for the off-treatment period.

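### The SAP's MRI safety table counts ARIA-H and lacunar infarct by presence on a double-blind scan, so lesions already there at entry can be mixed with new ones

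*SAP*

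**What the plan says.** SAP 6.4.3 gives the schedule: "All subjects will have an MRI during screening and after randomization at Months 6, 12, 24, 36 and 54", with provision for early termination. For each arm it then reports "The number and percentage of subjects with evidence of a finding at any time during the double-blind period and at each time point". The rows are ARIA-E, ARIA-H (microhemorrhages, macrohemorrhages, superficial siderosis), lacunar infarct, territorial infarct outside the cerebellum, and full-territory cerebellar infarct. The section also promises unspecified further summaries of ARIA-E and ARIA-H and a subject listing, and adds: "Similar analyses will be performed for the off-treatment period".

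Protocol 4.2 excludes subjects with "edema or effusion (ARIA-E) at screening" (criterion 15). No criterion names ARIA-H or lacunar infarct. Criterion 2 excludes brain disease beyond very early signs of AD or typical age-related change. Criterion 3 excludes other abnormalities that could cause a cognitive deficit, with vascular encephalopathy and large strokes as examples. Protocol 9.4.2.3 requires central MRI review before enrolment.

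Two SAP rules bear on the off-treatment reference. Section 2.3 says: "For assessments after last dose, use last observation before last dose as the reference time point". Section 2.4 sets the off-treatment baseline equal to the on-treatment end point, which "is defined as the last available post-baseline result among the on-treatment visits".

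**The concern.** Protocol 3.2.7 gives monitoring for ARIA as the reason for the safety MRIs. The reader of this table therefore wants to know how many subjects developed a lesion after starting treatment. A count of presence does not answer that when the lesion can persist from before treatment and its carriers are not clearly kept out. ARIA-E is excluded at entry, so presence on study is close to new occurrence. ARIA-H and lacunar infarct have no such named exclusion.

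The stake is readability and precision. To the extent that entry lesions got through, percentages would be higher in all arms, a true difference in new lesions would look smaller, and chance imbalance in entry lesions would add noise. Randomization gives no reason to expect the error to favour one arm.

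**Working it through.** **Does any passage supply the missing condition?**

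- SAP 2.3 puts days before Study Day 1 in the screening phase. The screening scan itself is not counted, but the same lesion read again later is.
- Protocol 11.10 contains no MRI safety analysis. SAP 4.1.2 takes only hippocampal volume from the baseline MRI, so no specified baseline table shows entry lesions by arm.
- The SAP conditions on baseline elsewhere: off-treatment liver criteria (6.1.1), vital signs (6.2), ECG (6.3), the C-SSRS increase criteria with a baseline-restricted denominator (6.4.2), and the dermatology listing (6.4.6). It does not do so for the neurological and physical examinations (6.4.4, 6.4.5).
- Comparison with screening is feasible. Every subject has a screening MRI, and Protocol 9.4.2.3 specifies identical pulse sequences throughout.

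**Off-treatment reference.** The first scheduled post-baseline MRI is at Month 6. A subject who stopped dosing earlier may have no post-baseline on-treatment MRI, hence no off-treatment baseline under 2.4. Section 2.3 would reach back to the screening scan. Section 6.4.3 does not say how either reference enters a presence count.

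**Size.** The documents give no lesion rates, so there is no plan figure to reproduce. What follows is illustration. Inputs:

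- n = 557/3 = 185.7 per arm (557 randomized, SAP 1; 1:1:1 allocation). This is an upper bound, because the number with a post-baseline MRI is not given.
- Assumed entry prevalence p0 of 2 to 25%.
- Assumed new-lesion risks iP = 2% (placebo) and iA = 6% (active), the same with or without an entry lesion.

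Formulas, if entry lesions are always seen again:

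- reported proportion r = p0 + (1 − p0)·i, so the reported difference is (1 − p0)(iA − iP)
- SE of the difference = sqrt{[rP(1 − rP) + rA(1 − rA)]/n}
- SD of chance imbalance in entry lesions = sqrt{2·p0(1 − p0)/n}
- share of counted placebo subjects with no new lesion = p0(1 − iP)/rP

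Counting new lesions only, with all subjects in the denominator: SE = sqrt{(0.02×0.98 + 0.06×0.94)/185.7} = 2.02 points, for a difference of 4.0 points and a ratio of 3.0. Restricting to lesion-free subjects replaces n by n(1 − p0).

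| p0 | Table shows (placebo vs active) | Difference | SE as written | SE, lesion-free only | Imbalance SD | Placebo share with no new lesion |
|---|---|---|---|---|---|---|
| 2% | 3.96% vs 7.88% | 3.92 | 2.44 | 2.04 | 1.45 | 50% |
| 5% | 6.9% vs 10.7% | 3.8 | 2.93 | 2.08 | 2.26 | 71% |
| 10% | 11.8% vs 15.4% | 3.6 | 3.55 | 2.13 | 3.11 | 83% |
| 25% | 26.5% vs 29.5% | 3.0 | 4.66 | 2.34 | 4.49 | 92% |

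Differences, SEs and SDs are in percentage points. At p0 = 10% the ratio falls from 3.0 to 15.4/11.8 = 1.31. If only 80% of entry lesions are seen again, the difference is multiplied by 1 − 0.8·p0: 0.96, 0.92 and 0.80 at 5, 10 and 25%. With an assumed 150 or 100 scanned subjects per arm, the imbalance SD at p0 = 10% is 3.5 or 4.2 points.

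The loss in the difference is small. The larger effects are the added noise and the share of counted subjects with nothing new.

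**The case against.** The table promises evidence of a finding, not incidence, so a persisting lesion is counted exactly as described, and the examination tables use the same convention. That is true of the wording. It does not make the table suited to the purpose that the protocol gives for these scans.

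The phrase about each time point could be read to include screening, which would show entry prevalence by arm. A new lesion may also be recorded as an adverse event (Protocol 12.1.1) and reach the treatment-emergent tables (SAP 6.1). The imaging charter, which is not among the documents, might define a finding as new. These points soften the concern, but none separates new from old lesions within a subject in this table, and 6.4.3 cites no charter rule.

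The strongest objection is that prevalence at entry may be low. Exclusions 2 and 3 are broad, scans were read locally and centrally, and nothing in the documents supports a value as high as 25%. This stands. A reader might infer that the reported percentages are in fact inflated in every arm, or that the table favours one arm. The documents support neither: the first depends on an unknown prevalence, and the second would need a chance imbalance.

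The presence-only version of the fix also has a cost. It misses a further lesion in a subject who already had one, and its SE is about 2.1 rather than 2.0 points at 10% prevalence.

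**Conclusion.** The point holds as a gap in the counting rule. As written, SAP 6.4.3 can report an ARIA-H or lacunar lesion present at entry as an on-study finding, and no other passage prevents it. The consequence is conditional. If such lesions passed the entry criteria, percentages would be inflated in all arms and the comparison of new lesions diluted by a factor of about 1 − p0 and made noisier, with no directional bias. If the entry criteria removed nearly all such subjects, the effect vanishes. Every magnitude above rests on assumed prevalence and risks and on an upper-bound arm size.

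The table is descriptive, in a study whose dosing has stopped, and no test or decision rule uses it. This is a low-cost improvement to one safety table, not a flaw in the trial's conclusions.

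**What to change.** In SAP 6.4.3, for ARIA-H and lacunar infarct (and the other infarct rows for consistency):

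- Add a count of subjects with a finding new or increased against the screening MRI, among subjects with a screening and at least one post-baseline MRI.
- If only presence was recorded, count absent at screening and present later, with subjects free of that finding at screening as the denominator. State that worsening in subjects with an entry lesion is then not captured.
- Show screening prevalence by arm, or a shift table.
- Name the screening MRI itself as the reference, not the baseline visit window. For rescreened subjects, Protocol 9.1.2 says "If MRI was completed within 6 months of randomization, it would not need to be repeated in most cases", while the baseline window in SAP 2.4 Table 1 opens at Day −120.
- For the off-treatment count, state one reference that reconciles 2.3 with 2.4: the last MRI before last dose, or the screening MRI if there is no on-treatment scan.

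The ARIA-E row can stay as written. The cost is SAP wording and a derived flag on MRI reads already collected, with somewhat smaller denominators. No new scans are needed.

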6.4.4. Neurological Examination

A neurological examination will be performed during screening; at randomization; after randomization at Month 6 and Month 12, then annually through Month 48, and at Month 54 (or early termination). The neurological examination includes an evaluation of mental status, cranial nerves, motor ability (including strength, tone, and involuntary movements), coordination (including finger-to-nose, gait, and postural reflexes), and sensation (including proprioception, cold, light touch, and deep tendon reflexes). The number and percentage of subjects with abnormal findings will be summarized by category and by treatment group for both on and off-treatment periods.

6.4.5. Physical Examination

Physical examination will be performed during screening; at randomization; after randomization at Month 6 and Month 12, then annually through Month 48, and at Month 54 (or early termination). The number and percentage of subjects with abnormal findings will be summarized by body system and by treatment group for both on and off-treatment periods.

6.4.6. Dermatological Examination

A dermatological examination will be performed during screening and after randomization at Month 12 (or early termination if no Month 12 examination).

The distribution of the dermatological examination result (normal; abnormal, not clinically significant; abnormal, clinically significant) will be summarized at screening, Month 12, and double-blind phase endpoint. A listing of subjects with changes from normal at screening to abnormal during the double-blind phase will be provided and will include the description of the abnormality.

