##### Nonclinical

Repeated-dose toxicity studies up to 6 months duration in the rat and up to 9 months duration in the dog were performed; additionally a 6-month carcinogenicity study in the transgenic Tg.rasH2 mouse was performed. In general, repeated dosing of atabecestat was well tolerated in all species. Target organs were limited and were mostly only affected at high doses.

Discoloration of the fur, ie, from dark-brown to paler cream or grey, was observed in the 6-month carcinogenicity study in the Tg.rasH2 mouse from approximately 3 months of dosing at dose levels of  $\geq 100$  mg/kg/day. Rochin et al. (2013) described the role of BACE-2 in melanogenesis with similar fur discoloration (depigmentation) in dark-colored mice. Therefore, it is likely that the discoloration, which showed at least partial recovery during a 3-month drug-free period, can be ascribed to BACE-2 inhibition by atabecestat. Standard histopathologic evaluation of the skin and of the pigmented parts of the eye (iris, retina), as well as ophthalmologic examination of the eye, did not reveal any relevant changes in this 6-month study. Similar changes cannot be detected in typically used albino animals (rats and mice), but in dog studies (eg, beagle dogs with colored fur), no change in fur color, no histological changes of the skin, and no changes of the pigmented parts of the eye were seen at either ophthalmologic or histopathologic examination at any dose level tested.

Based on the in vitro and in vivo safety pharmacology studies conducted, atabecestat has the potential to induce QTc prolongation and an increase in heart rate with an in vivo safety margin of approximately 9-fold (no observed effect level of 1,850 ng/mL after an oral dose of 10 mg/kg in the telemetered conscious dog Good Laboratory Practice [GLP] study) versus the exposure at a dose of 25 mg/day in humans (210 ng/mL at steady-state). Therefore an early thorough QT study was performed in the clinical program (see Clinical section below).

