#### **9.9.5. Dermatological Examination**

All subjects will undergo a comprehensive skin examination performed by a dermatologist (as defined in Section 9.1.2) during screening and again at Month 12 (or at the ET visit if subject withdraws from study or discontinues treatment prior to Month 12 assessment) to exclude the presence of skin lesions or depigmentation. A digital photograph of the frontal scalp, open eyes, and eyebrows will be collected by the dermatologist or a qualified designee to document changes noted by the dermatologist to monitor for dermatological safety. This is an essential requirement of the safety monitoring in the trial.

Whenever a skin lesion not previously documented is reported by the study subject, informant, investigator, or study personnel, and if deemed medically relevant, subject should undergo a dermatologic exam by a dermatologist. In addition digital images of the lesion will be acquired by the dermatologist or qualified designee at the time the lesion is discovered and at follow-up visits with a frequency which is deemed appropriate by the sponsor. As skin lesions may be temporary, the site personnel may consider documenting immediately at the site with a photograph in addition to referring the subject to the dermatologist. Duration of follow-up of newly documented skin lesions or depigmentation might extend beyond the double-blind treatment phase, as judged adequate by the sponsor to ensure the safety of participants in this study.

Lightening of hair and lightening of skin are AESIs in this study based on nonclinical studies conducted with atabecestat or reported findings for BACE knockout animals or other BACE inhibitors in development (see Section 12.3.1).

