6. SAFETY

All safety summaries will be presented for the on-treatment period and the off-treatment period,

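### The skin-examination listing omits new or worsened findings, including depigmentation, in subjects already abnormal at screening, and its endpoint does not match the SAP's on- and off-treatment periods

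*SAP*

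**What the plan says.** SAP 6.4.6 plans two outputs for the dermatological examination. The first is a table of the overall result in three grades (normal; abnormal but not clinically significant; abnormal and clinically significant), which "will be summarized at screening, Month 12, and double-blind phase endpoint". The second is a listing: "A listing of subjects with changes from normal at screening to abnormal during the double-blind phase will be provided". The listing carries the description of the abnormality; the table does not.

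Protocol 4.2, exclusion criterion 14.1, bars hypopigmentation abnormalities of the skin such as vitiligo, with an exception: "Small localized lesions other than vitiligo are allowed". Protocol 9.9.5 gives every subject a full skin examination by a dermatologist at screening and again at Month 12, or "at the ET visit if subject withdraws from study or discontinues treatment prior to Month 12 assessment". Lightening of skin and of hair are adverse events of special interest (Protocol 12.3.3 and Attachment 2).

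On periods, the opening line of SAP 6 states: "All safety summaries will be presented for the on-treatment period and the off-treatment period". SAP 2.3 places every day from Day 1 in the double-blind phase, with no cut at last dose.

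**The concern.** The examination looks for skin lesions and depigmentation, and it is the only skin assessment that every subject receives on a schedule. What counts is the change since screening. The listing instead selects on the screening grade, so it leaves out everyone who was not normal at entry. That includes any subject admitted with a small pale lesion graded abnormal, against which a later pigment change would have to be judged.

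Timing matters as well. After dosing stopped on 17 May 2018, subjects stayed in the double-blind phase untreated for about 3 to 6 months and then had an early termination visit (Protocol 1.1). For a subject who had not reached the Month 12 examination, the only post-screening examination could fall well after the last dose. A reader of the listing or of the endpoint row needs to know whether a finding was made on or off drug.

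**Working it through.** No sample size or error rate is involved. The check traces which changes each output can show, and then compares the SAP's rules on periods.

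**1. Which changes are visible.** Three grades at screening and three later give 3 × 3 = 9 possible transitions.

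| Screening → later | In the listing? | Seen in the three-grade table? |
|---|---|---|
| Normal → either abnormal grade (2 transitions) | Yes, with description | Yes |
| Not significant → significant | No | Counts shift, but without description or type |
| Same abnormal grade, with a new finding (2 transitions) | No | No |
| Significant → not significant, with a new finding of another kind | No | Shown only as an improvement |

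The other three transitions end in normal. All 6 transitions that start from an abnormal grade are outside the listing. The table gives counts at each time point, not paired changes, so a worsening in one subject can be offset by an improvement in another. Protocol 11.10 calls for frequency tabulations of abnormalities at each time point. SAP 6.4.6 tabulates grades, so hypopigmentation cannot be told from any other skin finding. It also does not name treatment group, as SAP 6.4.4 and 6.4.5 do.

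**2. Can a subject enter abnormal?** Yes. Criterion 14.1 allows minor circumscribed lesions that are not vitiligo. The listing rule also turns on any abnormal screening grade, whether or not pigment is involved.

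**3. Other routes to the outputs.** The SAP's Adverse Events section summarises hypopigmentation events with no condition on the screening result. Those events are the ones the investigator marks on the adverse event page, and Attachment 2 makes that entry conditional on the site judging the finding to be an adverse event.

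**4. Periods.** SAP 2.4 labels each post-baseline visit on- or off-treatment by the treatment end date, and defines two endpoints: End point (On-Trt) and End point (Off-Trt). Double-blind phase endpoint is neither. To illustrate, take a last dose on 17 May 2018 and an early termination examination on 17 September 2018, the planned last-patient-out date:

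- Days elapsed: 14 + 30 + 31 + 31 + 17 = 123.
- Analysis Day counted from treatment end: 123 + 1 = 124.
- Window in SAP Table 1: Month 4 (days 107 to 134), labelled off-treatment. The Month 12 window is days 334 to 410.

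SAP 2.3 also contains a bullet that counts all days from first dose. On that reading the window changes, but the off-treatment label stays. The Month 12 row is therefore separable either way. The endpoint row is not settled, and the listing, which is not a summary, falls outside the wording of SAP 6.

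**5. Reference for the off-treatment result.** Under SAP 2.4 the off-treatment baseline is the last on-treatment post-baseline result. A subject whose only post-screening skin examination is at early termination has none, so the general off-treatment rule cannot be applied without naming screening as the reference.

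**The case against.** The strongest reply is that the plan does not rely on this listing. Lightening of skin or hair must be reported within 24 hours whatever the screening result, with dermatology consultation and photographs (Attachment 2). A previously undocumented lesion judged medically relevant leads to a dermatologist's examination and images (Protocol 9.9.5). Hypopigmentation events are summarised separately. This stands, so a reader should not infer that depigmentation in these subjects is lost to the whole plan. What remains is that this route needs a site decision to report an adverse event, whereas the scheduled examination does not.

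A reader might also infer that on-drug and off-drug examinations are pooled. The documents do not settle that. SAP 6 and the visit labels in SAP 2.4 require a split of summaries. For the table the fault is an undefined term that conflicts with that rule. For the listing it is the absence of any stated split. Nor is the table blind to everything: a move from not clinically significant to clinically significant does change its counts.

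No size can be attached. Criterion 14.1 screens out the baseline findings most easily confused with a drug effect, and nothing shows that abnormal screening results are common. The SAP's 447 of 557 subjects (447/557 = 80%) with 12 months of treatment or less counts treatment duration, not off-drug examinations. The remark on fur discoloration "which showed at least partial recovery during a 3-month drug-free period" concerns mice and does not show that a human pigment change would fade before the early termination visit.

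**Conclusion.** The point holds for the skin-examination outputs in SAP 6.4.6. The listing cannot show a new or worsened finding in a subject graded abnormal at screening, and a change within the same grade is also invisible in the table. Such a finding reaches the outputs only as a reported adverse event. The listing lacks a split at last dose, and the endpoint label needs to be reconciled with SAP 2.4 and SAP 6.

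The conclusion rests on applying the listing rule as written and on subjects being able to enter with an abnormal skin grade, which criterion 14.1 permits. How many subjects are affected is unknown, because the documents do not give the share abnormal at screening. After early cessation the safety analysis is descriptive and no formal claim about pigment depends on this listing. It is a modest gap in describing an event of special interest, and worth closing because doing so is cheap.

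**What to change.** In SAP 6.4.6:

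- List, by treatment group, every subject with a new or worsened finding versus screening, including abnormal-to-abnormal. Show the screening and post-baseline descriptions, a hypopigmentation flag, and the examination day relative to last dose.
- Add a shift table from screening in the three grades by treatment group, and a count by arm of subjects with new or worsened hypopigmentation.
- Replace double-blind phase endpoint with the on-treatment and off-treatment endpoints of SAP 2.4, using screening as the reference for both.

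This uses data already collected. The cost is SAP wording, a longer listing, and a comparison of text descriptions for subjects abnormal at both times. That comparison should be done blind to treatment, with the meaning of new or worsened fixed beforehand.
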